- 14 Cancer that is not considered cured, except basal cell or squamous cell carcinoma of the skin (cured defined as no evidence of cancer within the past 5 years)
- 15 Any serious medical condition that is likely to impede successful completion of the study, such as certain mental disorders, hypersensitivity to onabotulinumtoxinA or anesthetics used in the study, syncope
- 16 Daily use of a pad or device for incontinence required
- 17 Interested in future fertility
- 18 PVR greater than 350 ml
- 19 Serum prostate specific antigen level greater than 8 ng/ml (Hybritech). For those with a PSA between 4-8 ng/ml, the PSA elevation must be considered to

- be from a benign cause in the opinion of the PI. This decision can be based on PSA velocity, previous TRUS biopsy, percent free PSA, or other clinical estimations in keeping with sound urologic care
- 20 No alpha-blockers in the past 7 days before biopsy.
 - 21 Has taken phenylephrine, pseudoephedrine, imipramine, an anticholinergic, or cholinergic medication within the past 2 weeks
 - 22 Has taken estrogen, androgen, any drug producing androgen suppression, or anabolic steroids within the past 4 months
 - 23 Is taking aminoglycosides or any drug that interfere with neuromuscular transmission. Eaton-Lambert syndrome, hemophilia, hereditary clotting factors deficiency, or bleeding diathesis
 - 24 Must be off aspirin, NSAIDS, and Coumadin for 7 or more days prior to onabotulinumtoxinA injection
 - 25 Enrolled in another treatment trial for any disease within the past 30 days

VIII DESIGN

This Phase 2 clinical research trial is a double-blind, randomized, placebo-controlled, parallel-group study to compare the treatment effects of onaBoNT-A 200 U versus 0.4 mg per day of oral tamsulosin in male veterans diagnosed with moderate to severe LUTS (AUASS equal to or greater than 8) associated with BPH. A total of 74 volunteers will be recruited to participate in this clinical trial. Volunteers will include only males who are greater than 50 years of age and diagnosed with LUTS associated with BPH. They are veterans who visit the MEDVAMC. There are no eligibility restrictions as to race or ethnicity.

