Transition zone biopsies will be performed at Visit 2, 30 days before treatment, and again at 3 months post-treatment. A total of 6 biopsy cores (i.e. 3 cores from the left and right transition zone) will be obtained from each volunteer. Prostate biopsy cores will be rapidly snap frozen in liquid nitrogen in coded and labeled containers and sent to [name] laboratory located at University of Texas Health Science Center - Houston Medical School for further processing.

A Randomization

Volunteers will be randomized using a blocked randomization approach by the MEDVAMC Research Pharmacy to either: ARM 1: onaBoNT-A 200 U prostate injection and placebo oral capsule daily or ARM 2: Placebo prostate injection (saline) and tamsulosin 0.4 mg capsule daily. Subjects will be randomized into one of the two treatment arms, using a block size of 4. The order in which the treatments are assigned in each block is randomized and this process is repeated for consecutive blocks of subjects until all subjects are randomized. This process ensures that after every fourth randomized subject, the number of subjects in each treatment group is equal. The MEDVAMC will prepare both pills (i.e. tamsulosin and placebo pill) and injections (i.e. onaBoNT-A and placebo saline injection) so that the study subject, investigator and all personnel treating or evaluating the subject will be blinded to treatment allocation.

B Schedule Of Events During Treatment Protocol

Tests/Time	Visit 1: Screening	Visit 2: Biopsy	Visit 3: Injection (4 weeks Post- biopsy ± 3 days)	Visit 4: Telephone Visit (Day 3 Post Prostate Injection)	Visit 5: Telephone Visit (1 Week Post- Injection ± 3 days)	Visit 6: (4 Weeks Post- Injection ± 3 days)	Visit 7: End of Study (3 months Post Injection ± 3 days)
Physical with DRE	X						X
Medical History	X						
Vital signs	X	X	X			X	X
Flowrate	X					X	X
PVR	X					X	X
PSA	X						X
CBC /platelet count	X						
Urinalysis (dipstick)	X	X	X			X	X
Biopsy(Transrectal Ultrasound Guided - TRUS)		X					X
Prostate Volume		X					X
Antibiotic		X	X				X
Fleets Enema		X	X				
Anesthesia (periprostate block)		X	X				
onabotulinumtoxin A or saline injection via TRUS			X				
Informed Consent	X						
Antibiotic dispensing	X	X				X	
Instructions to stop alpha blocker meds 7 days prior to biopsy	X						
Drug/Placebo dispensing			X			X	
Drug/Placebo accountability						X	X
AUA Symptom score	X					X	X
BPH Impact Scale	X					X	X
Bladder Function	X					X	X
Erectile Function	X					X	X

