- C Urine specimens collected for dipstick analysis during the screening visit are routine for patients with BPH and LUTS and will be handled according to standard of practice. The test results will be included in the subject's research and medical charts.

X. STATISTICAL ANALYSIS

The primary endpoint, change in AUASS score from baseline to 3 months, between the onaBoNT-A and tamsulosin groups will be analyzed using the 2-sided independent t-test.

Baseline measures of the data such as age and ethnicity as well as secondary endpoints will be examined using summary statistics to determine if any differences exist between the 2 study groups.

Graphical methods will be used to access distributional properties of the secondary endpoints (urinary flow rate, serum PSA, prostate volume symptom relief, post-void residual, BPH impact score, Bladder Function, Erectile Function and Ejaculatory Function questionnaires). If extreme departures from normality are found, use of non-parametric analytical methods such as the Wilcoxon rank-sum test or transformation of the data will be considered. Questionnaire scores will be examined for reliability using Cronbach's alpha. The distributions of the scores will be examined to see if they are evenly distributed around the mid-point of the scales or are clustered at the top or bottom of the scales (ceiling or floor effect). If strong ceiling or floor effects are found, this could limit the usefulness of these measures. Changes in these secondary endpoints will be assessed using either the independent t-test or its non-parametric equivalent, the Wilcoxon rank sum-test. Statistical analysis will be done using SAS, version 9.2 (SAS Institute, Cary NC).

The endpoints apoptotic index, proliferation index, nerve density, stromal reactive indexes, and vessel density, will be checked for their distributional properties using the methods described for the data collected in Aim 1. Change from baseline to 3 months will be analyzed using either the 2 sided t-test or the Wilcoxon rank sum test.

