Mean AUA score reduction in the alpha blocker group is expected to be at most 9.6 with a standard deviation of 6.3 based on published results of a randomized trial comparing tamsulosin versus placebo.²⁹ However, that same study showed a strong pill placebo effect with a mean reduction of 5.5, resulting in a treated reduction of 4.1 above the placebo group. Another study¹³, comparing botulinum toxin to placebo, showed a mean score reduction in the botulinum group of 15.2 and no placebo change. For our study, we will assume a mean reduction of 15.2 in the onaBoNT-A group which is 9.7 more than the pill placebo effect, a mean reduction of 9.6 in the alpha blocker group and a standard deviation of 6.3 for both groups. Based on these assumptions, a sample size of 29 subjects per group will achieve 90% power to detect a difference of 5.6 with an alpha level of 0.05 using the 2-sided independent t-test. Sample size calculations were done using PASS 2008 software (Hintze, J. (2008). NCSS, LLC. Kaysville, Utah. www.ncss.com).

The drop-out rate in the alpha-blocker study was as large as 20% and our own experience with onabotulinumtoxinA (onaBoNT-A) in the MIST-2 trial has demonstrated a dropout rate of 14%. So adjusting our sample size for an expected dropout rate of 20%, we will enroll 37 patients into the onaBoNT-A and tamsulosin groups for a total of 74 patients. To address some of the problems with possible attrition bias, we will use intent to treat analysis and patients will be kept in the study as long as possible even if they are no longer on treatment. We will also compare results between the intent to treat groups and the subjects who completed treatment to determine if differences exist.

XII. RETENTION AND DROPOUT/WITHDRAWAL

Minimal dropout or loss to follow-up is expected in this cohort, especially given the short follow-up. However, if a patient drops out before 4 weeks, he will be replaced so that the required sample size is realized. For purposes of tracking the feasibility of conducting a trial of treatment with onaBoNT-A, reasons for dropout or withdrawal will be documented.

XIII. CRITERIA FOR DISCONTINUING THE STUDY

- A Subjects unable to tolerate [tamsulosin or] onaBoNT-A due to side effects.
- B Subjects can request removal from the study for any reason at any time.
- C Subjects may be withdrawn at any time at the discretion of the investigator for safety, compliance, or other reasons.

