A discontinuation occurs when an enrolled subject ceases participation in the study, regardless of the circumstances, prior to completing the protocol.

The reasons for a subject discontinuing from the study will be recorded in the Case Report Form.

XIV. DATA ANALYSIS

Analysis will begin with descriptive statistics. Implausible and missing values will be identified and double-checked for accuracy. Parametric methodology will be used unless measurements have tested positive for violation of normality assumption. The differences between the study subjects groups will be evaluated using the paired-samples t-tests. The clinical outcomes will be compared using Fisher's test. The criterion for significance (alpha) has been set at 0.05. All tests are 2-tailed, which means that an effect in either direction will be interpreted. Analysis will be conducted using SPSS 17.0. ("SPSS Statistics 17.0", SPSS Inc., Chicago, IL, 2008).

XV. RISKS AND DISCOMFORTS

- A BOTOX®: It is expected that some participants may have some or all of the following side effects when given BOTOX®. Other side effects may occur which were not seen before. Side effects are usually temporary and manageable. However, it is possible they could cause serious disease or death. The study may include risks that are unknown at this time.

There have been rare reports of serious and/or immediate or even deadly abnormally sensitive reactions after treatment with BOTOX. These reactions include allergic reaction, skin rash, itching, swelling, and difficulty in breathing.

It is a rare possibility that the injection of BOTOX® could lead to botulism. The classic symptoms of botulism include double vision, blurred vision, drooping eyelids, slurred speech, difficulty swallowing, dry mouth, and muscle weakness. The doctor's examination may reveal that the gag reflex and the deep tendon reflexes like the knee jerk are decreased or absent.

There have been rare reports of sudden death, sometimes associated with difficulty in swallowing or pneumonia. There have also been rare reports of heart problems (including irregular heart beats and heart attack, some resulting in death). Some of these patients were already at risk for heart disease. It is not known if BOTOX actually caused these problems.

It should not be used when infection is present at the injection site or in people known to be abnormally sensitive to BOTOX.

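### Section XIV assigns between-group differences to paired t-tests, but the arms are unmatched and Sections X and XI use the independent t-test

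*Combined protocol and SAP*

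**What the plan says.** Three sections of the combined protocol and SAP name a test for comparing the arms.

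- **Section X, Statistical Analysis.** The primary endpoint, change in AUA symptom score from baseline to 3 months, "between the onaBoNT-A and tamsulosin groups will be analyzed using the 2-sided independent t-test". For the secondary endpoints: "Changes in these secondary endpoints will be assessed using either the independent t-test or its non-parametric equivalent, the Wilcoxon rank sum-test". The tissue indexes get a 2-sided t-test or the Wilcoxon rank-sum test.
- **Section XI, Sample Size.** The trial is sized to "detect a difference of 5.6 with an alpha level of 0.05 using the 2-sided independent t-test".
- **Section XIV, Data Analysis.** "The differences between the study subjects groups will be evaluated using the paired-samples t-tests". No endpoint is named, no pairing is defined, and Section X is not mentioned.

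Section VIII describes a "double-blind, randomized, placebo-controlled, parallel-group study". On allocation it says: "Subjects will be randomized into one of the two treatment arms, using a block size of 4".

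**The concern.** A paired t-test analyses differences within linked pairs. Here each man is in one arm only. Blocks of 4 balance the numbers allocated but do not define pairs, and no matching is described anywhere. The Section XIV test therefore has no defined input. It also requires the same number of men in each arm, which the plan does not ensure.

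The plan thus contains two different rules for comparing the arms and no statement of precedence. Section XIV comes later, is headed as the data analysis section, and names different software (SPSS 17.0, against SAS 9.2 in Section X), so an analyst could take it as an instruction in its own right. Two misuses are possible: pairing unrelated men by row order, or running pre/post tests within each arm and presenting them as the comparison between arms.

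**Working it through.** **Inputs.** From Section XI: mean reductions of 15.2 and 9.6 (difference 5.6), SD 6.3 in both groups, two-sided alpha 0.05, 29 per group for 90% power, dropout of 20% (14% also quoted), 37 per arm and 74 in total, and a pill-placebo reduction of 5.5. From Section VIII: block size 4.

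**1. The plan's own sample size.** For two independent samples the noncentrality is 5.6 / (6.3 × √(2/29)) = 3.385. With 56 df the critical value is 2.003 and the power is 0.914. The exact calculation needs 27.6, so 28 per group; the stated 29 for 90% is slightly generous and acceptable. Dropout: 29 / (1 − 0.20) = 36.25, rounded up to 37 per arm, 74 in total. The stated figures stand on the independent t-test.

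**2. Can the paired test be run across arms?** Treat the numbers with 3-month data as two independent Binomial(37, 1 − dropout) counts, with no imputation. P(unequal) = 1 − Σ P(k)², summed over k = 0 to 37:

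| Dropout | Source | P(arms unequal) |
|---|---|---|
| 20% | Section XI | 0.884 |
| 14% | Section XI | 0.866 |
| 10% | assumed | 0.844 |
| 5% | assumed, to allow for replacement of early dropouts | 0.781 |

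Equal numbers are not assured at allocation either. 74 = 18 × 4 + 2, so if exactly 74 men are randomized the last block is half filled. Given the first of those two assignments, one of the three remaining places in the block is for the same arm, so the chance of a 38/36 split is 1/3.

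**3. If the arms happen to be equal (29 each).** Pairing unrelated men gives differences with SD 6.3 × √2. The noncentrality is again 3.385, but with 28 df the critical value is 2.048 and the power is 0.904. In 200,000 simulated trials per setting:

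- Type I error was 0.050 for both tests.
- At the planned difference, two random pairings of the same data disagreed at the 0.05 level in 3.6% of trials, and one pairing disagreed with the independent test in 2.6%.
- Where the independent p-value lay between 0.03 and 0.07 (about 6% of trials at the planned difference), two pairings disagreed in 42%.

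**4. If the sentence means pre/post within each arm.** Take the 5.5-point pill-placebo change, apply SD 6.3 (an assumption, because Section XI gives that SD for the alpha-blocker group), and use 29 men. The noncentrality is 5.5 / (6.3/√29) = 4.70, and the test is significant with probability 0.995. A change of placebo size would nearly always be significant within an arm, so such a test says nothing about the difference between arms.

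**The case against.** The strongest reply is that this is a drafting slip with little consequence. Section X names the primary endpoint and its test, Section XI powers the trial on that test, and Section XIV is one generic sentence that names no endpoint. A specific rule stated twice should prevail over a general one, and a cross-arm paired test without a pairing rule is hardly a usable alternative. For the primary endpoint most of this stands: the intended test can be identified. It does not remove the error, because the plan sets no precedence and the Section XIV wording covers all differences between groups.

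The probabilities of unequal arms also depend on the dropout model. The plan calls for intent-to-treat analysis, keeps men in the study when off treatment, and replaces those who leave before 4 weeks. Men off treatment may still give 3-month data, and with replacement the number randomized may exceed 74, so the 1 in 3 figure holds only for exactly 74. This is fair: the percentages are illustrations, not the plan's expectation. The direction holds, since none of these provisions guarantees equal arms and 5% dropout still gives 78%.

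Finally, nobody proposes pairing by row order, and the 42% applies to about 6% of trials. That is correct; the overall figure is 3.6%. The simulation shows only that the result would depend on an arbitrary choice.

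**Conclusion.** The concern holds. Section XIV states a between-arm test that does not fit an unmatched parallel-group design and contradicts the test on which the trial is analysed in Section X and powered in Section XI. It is an error in the text, not a missing detail, and should be corrected before analysis.

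The case rests on the nature of the error. With equal arms the cost is about one point of power (0.914 against 0.904) and type I error is unaffected. With unequal arms, which is the likely outcome under independent dropout, the rule cannot be applied to all the data. The within-arm reading rescues nothing, because it does not compare the arms. The simulated figures assume normal data with the Section XI means and SD.

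**What to change.** Replace the paired-samples sentence in Section XIV with a statement that all between-arm comparisons of continuous endpoints follow Section X: the 2-sided independent t-test for the primary endpoint, the independent t-test or Wilcoxon rank-sum test for the secondary endpoints, and the 2-sided t-test (stated to be the independent form) or Wilcoxon rank-sum test for the tissue indexes. If paired tests are kept, say that they apply only to change within an arm, are descriptive for the clinical endpoints, and are not evidence of a difference between arms. Section IX also plans before-and-after comparisons of gene expression; if a paired method is meant there, name it there.

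As tidying in the same edit, list the binary outcomes to which Fisher's test applies and name one software package.

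The cost is wording only. The sample size stays at 29 per arm, 37 after dropout, and power and data collection are unchanged.
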